9.2 Discussion of Study Design, including the Choice of Control Group

The study is designed to investigate the efficacy, safety, and tolerability of a capsule formulation of ganaxolone administered as 1800 mg per day in divided (BID) doses in

the adult epilepsy population with drug-resistant epilepsy consisting of POS, compared to placebo. A secondary goal is to evaluate blood levels, efficacy and tolerability of ganaxolone 1200 mg/d and 1800 mg/d in a separate cohort of subjects. Completers in both cohorts are eligible to enter into a one year, open-label, flexible dose continuation phase.

The two-cohort design permits evaluation of the relative blood levels of 1200 mg/d and 1800 mg/d doses of ganaxolone in Cohort 1, and while Cohort 2, evaluates efficacy, tolerability and safety of the 1800 mg/d dose in an appropriately powered sample size for a 12 week duration that is consistent with regulatory standards for registration studies.

Administration of study drug as adjunctive therapy to background AEDs permits comparison with placebo while maintaining the subjects on prior anticonvulsant therapy.

9.3 Selection of study population

9.3.1 Number of Subjects

Approximately 525 subjects will be screened to randomize approximately 46 subjects into Cohort 1 and approximately 359 subjects into Cohort 2 at a 1:1 ratio of ganaxolone to placebo, assuming a screen-failure rate of 15%. It is estimated that approximately 320 subjects will complete the 14-week double-blind phase of Cohort 2, which assumes approximately 10% discontinuation rate.

9.3.2 Inclusion Criteria

Subjects must meet all inclusion criteria to be eligible for entry in the study. The option for re-screening of subjects who do not meet all criteria must be discussed with the Medical Monitor.

1. Able to give informed consent in writing, or have a legally authorized representative able to do so (if permitted in your country/region), after being properly informed of the nature and risks of the study and prior to engaging in any study-related procedures.

2. Willing to enter and participate for the full term of 9 or 14-week double-blind phase and willing to enter into the open-label phase.
3. Male or female outpatients ≥ 18 years of age at time of consent.
4. Have a confident diagnosis of drug-resistant epilepsy with POS with or without secondary generalization (classified according to International League Against Epilepsy Guidelines [Guy, 1981] and as determined by secondary review by the Epilepsy Consortium) for ≥ 2 years and is having POS despite having been treated in the past with ≥ 2 approved anti-epilepsy drugs (AEDs) either alone or in combination at adequate doses for a sufficient length of time in the opinion of the investigator. Diagnosis should have been established by clinical history, electroencephalogram (EEG) or video EEG with results consistent with partial-onset epilepsy, and computerized tomography (CT) or magnetic resonance imaging (MRI) of the brain to rule out progressive structural lesions within the last 10 years. For Poland, a CT or MRI of the brain to rule out progressive structural lesions should be performed within 2 years prior to screening visit.
5. Based on documented history of POS, the investigator judges that the subject is likely to have 3 or more POS* during any 4-week period prior to study treatment, i.e., rarely falls below that threshold with usual fluctuations. Further, the pattern of seizures makes it unlikely the subject will have 21 seizure-free days in any 4-week period prior to study treatment.

* POS includes complex partial seizures [CPS], and simple partial seizures [SPS] with motor expression. Partial seizures may be seizures secondarily generalized [SGTC]. Subjects who only have simple partial seizures without any observable motor component will NOT be eligible to participate in this study.

6. Currently being treated and maintained with a stable regimen of 1, 2, or 3 AEDs for ≥ 1 month prior to the screening visit, without a foreseeable change in dosing

- for the duration of the double-blind phase of the study (AEDs may be adjusted during the open-label phase of the study).
- a. Barbiturates: If the subject is taking barbiturates (e.g., phenobarbital), the dose of the barbiturate must have been stable for ≥ 3 months prior to the screening visit.
 - b. Vagus Nerve Stimulator (VNS): VNS will not be counted towards the number of concomitant AEDs. Subjects with surgically implanted VNS will be allowed to enter the study provided that all of the following conditions are met:
 - i. The VNS has been in place for ≥ 1 year prior to the screening visit
 - ii. The settings must have remained constant for ≥ 3 months prior to the screening visit and remain constant throughout the study
 - iii. The battery is expected to last for the duration of DB Phase I (9 or 14 weeks) of the study
 - c. Benzodiazepines: The chronic use of a benzodiazepine as a concurrent AED is permitted as long as the dose has been stable for ≥ 1 month prior to the screening visit and remains constant throughout the study. See Section 9.4.10 for use of benzodiazepines for seizure rescue or for other indications.
 - d. Felbamate: The use of felbamate is allowed provided that the subject has been maintained on a stable dose of felbamate for ≥ 18 months, and has had stable liver function (AST/ALT) and hematology during the course of treatment, and is expected to remain constant throughout the study.
 - e. Perampanel: The use of perampanel is allowed provided that the subject has been maintained on a stable dose of perampanel for > 3 months and has not experienced any serious psychiatric and behavioral reactions such as hostility- and aggression- related adverse reactions.
7. Able and willing to maintain an accurate and complete daily written seizure calendar or has a caregiver who is able and willing to maintain an accurate and complete daily written seizure calendar.

8. Able and willing to take drug with food twice daily. Ganaxolone must be administered with food.
9. Sexually active women of childbearing potential (WCBP) must be using a medically acceptable method of birth control and have a negative qualitative serum β -human chorionic growth hormone (β -HCG) pregnancy test from a blood sample collected at the screening visit and negative urine pregnancy tests at baseline line and subsequent visits. A woman of childbearing potential is defined as a female who is biologically capable of becoming pregnant. A medically acceptable method of birth control includes intrauterine devices in place for at least 3 months, surgical sterilization, or adequate barrier methods (e.g., diaphragm and foam). An oral contraceptive alone is not considered adequate for the purpose of this study. Use of oral contraceptives in combination with another method (e.g., a spermicidal cream) is acceptable. In subjects who are not sexually active, abstinence is an acceptable form of birth control and β -HCG will be tested per protocol. Birth control should be continued for a minimum of 3 days after the last dose of study drug.

9.3.3 Exclusion Criteria

1. Have had previous exposure to ganaxolone.
2. Known sensitivity or allergy to any component in the study drug, progesterone, or other related steroid compounds.
3. Exposure to any investigational drug or device ≤ 30 days prior to screening, or plans to take another investigational drug at any time during the study.
4. Time of onset of epilepsy treatment < 2 years prior to enrollment
5. Have generalized epilepsy, such as Lennox-Gastaut syndrome, juvenile myoclonic

- epilepsy, absence epilepsy, or non-epileptic seizures within the last 12-month period prior to study entry.
6. Have less than 3 POS seizures in a 28-day period or more than 21 consecutive seizure-free days during the 8-week baseline period.
 7. Have only simple partial seizures without any observable motor component.
 8. Have innumerable seizures or status epilepticus within the last 12-months prior to screening.
 9. Have more than 100 POS total (complex partial seizures [CPS] only + simple partial seizures [SPS] with motor (both types with or without secondary generalized tonic-clonic seizures [SGTC])) per each 4-week baseline period.
 10. Seizures secondary to illicit drug or alcohol use, infection, neoplasm, demyelinating disease, degenerative neurological disease, or central nervous system (CNS) disease deemed progressive, metabolic illness, or progressive degenerative disease.
 11. Current use of vigabatrin is not permitted, as well as prior use of vigabatrin without stable visual fields tested prior to screening. If used during the last 12 months two visual fields tests are required.
 12. Current use of ezogabine (retigabine; Potiga; Trobalt) is not permitted. Subjects who may have used this agent in the past should have been off this medication for at least 3 months prior to screening and should have had a documented normal fundoscopic exam by an ophthalmologist.
 13. Are planning surgery, or to be evaluated for surgery, during the 9 or 14-week double-blind phase to control seizures including those subjects who are considering implantation of a VNS device.

14. Are suffering from acute or progressive neurological disease, moderate or severe psychiatric disease, or severe mental abnormalities that are likely to require changes in pharmacotherapy during the 9 or 14-week double-blind portion of the study or interfere with the objectives of the study or the ability to adhere to the protocol requirements.
15. Have active suicidal plan/intent, or have had active suicidal thoughts in the past 6 months.
16. Have a history of an actual suicide attempt in the last 5 years or more than 1 lifetime actual suicide attempt as classified by the Columbia-Suicide Severity Rating Scale (C-SSRS).
17. Have a positive urine drug screen at Screening or meet criteria for current or historical Substance Use Disorder (DSM-V criteria) within the past 5 years. As with other AEDs, the use of alcohol is not advised.
18. Have any medical condition that, in the investigator's judgment, is considered to be clinically significant and could potentially affect subject safety or study outcome, including but not limited to: clinically significant cardiac, renal, pulmonary, gastrointestinal, hematologic or hepatic conditions; or a condition that affects the absorption, distribution, metabolism or excretion of drugs.
19. Have Alanine transferase (ALT; SGPT) or Aspartate transferase (AST; SGOT) levels >3 times upper limits of normal (ULN), or total bilirubin >1.5 time ULN at the screening and baseline visits.
20. Have a history of malignancy within the past 2 years, with the exception of basal cell carcinoma.
21. Are currently following or planning to follow a ketogenic diet.

22. Use of dietary supplements or herbal preparations are not permitted if subject has been using them consistently for less than 6 months prior to screening, or does not plan on remaining on stable doses for the duration of the double-blind phase. Use of St. John's Wort is not permitted (See [Section 9.4.10](#): Excluded, Prior, and Concomitant Medications).
23. Females who are pregnant, currently breastfeeding or planning to become pregnant during the duration of the study.
24. A history of chronic noncompliance with drug regimens.
25. Inability to withhold grapefruit and grapefruit juice from diet during the entire clinical trial (See [Section 9.4.11](#): Excluded, Prior, and Concomitant Medications).

9.3.4 Removal of Subjects from the Study

9.3.4.1 Criteria for Withdrawal

All subjects reserve the right to withdraw from the clinical study at any time, as stated in the informed consent form (ICF). The Investigator may discontinue subjects from the clinical study for any of the following reasons:

1. Post-treatment QTc interval >500 msec or uncorrected QT interval >600 msec; for subjects with bundle branch block, post-treatment QTc >530 msec based on average QTc value of triplicate ECGs. A subject with a post-treatment increase in QTc of >60 msec from Baseline must also be withdrawn.
 - a. If the initial electrocardiogram (ECG) indicates a QTc interval outside of these limits, then 2 additional ECGs should be collected and the average QTc value of these 3 ECGs will be used. If the average values of the triplicate ECGs exceed the stated limits, the subject must be withdrawn.
2. Subject is found to have entered the clinical investigation in violation of the protocol;

3. Subject requires the use of an unacceptable or contraindicated concomitant medication;
4. Use of benzodiazepines as rescue for innumerable seizure clusters more than two times during 9 or 14-week DB phase, or more than once in a 28-day period must be discontinued;
5. Use of benzodiazepines as rescue for innumerable seizure clusters more once in a 28-day period during the Open-Label Phase, Investigator should consider discontinuation;
6. Subject's condition changes after entering the clinical investigation so that the subject no longer meets the inclusion criteria or develops any of the exclusion criteria;
7. Subject is noncompliant with procedures set forth in the protocol in an ongoing or repeated manner;
8. Subject experiences an adverse event (AE) that warrants withdrawal from the clinical investigation;
9. It is the Investigator's opinion that it is not in the subject's best interest to continue in the study;
10. Any subject who exhibits any of the following will be immediately withdrawn from the clinical investigation:
 - a. Clinically significant worsening of seizures as judged by Investigator or subject such that treatment outside of the protocol is assumed to be in the subject's best interest.
 - b. Two episodes of generalized tonic-clonic seizures (GTCS) if not present at baseline.
 - c. Status epilepticus at any time during the clinical investigation.
 - d. Any Suicidal Behavior as classified by the Columbia Suicide-Severity Scale (C-SSRS) or a "yes" answer to question 4 and 5 in the Suicidal Ideation section of the C-SSRS. These patients should be referred to psychiatric evaluation immediately.
11. Any subject who has the following liver enzyme findings should be immediately contacted and instructed to stop the study drug or start down titration of the study drug

- a. ALT or AST > 8 x ULN
- b. ALT or AST >5 x ULN for more than 2 weeks
- c. ALT or AST > 5 x ULN and total bilirubin >2 x ULN
- d. ALT or AST >3 x ULN with the appearance of fatigue, nausea, vomiting, right upper quadrant pain or tenderness, fever, rash or eosinophilia

Patients with ALT or AST > 3 x ULN but <8 x ULN and no clinical signs and symptoms indicating liver dysfunction can, at the discretion of the investigator, continue the intake of study drug with close monitoring.

All patients who fall into either category (patients who must discontinue the study drug [a, b, c and d] and who may continue the study drug with close monitoring) must be brought back to the study center without any delay, the next day if possible, but no later than 72 hours after the study results have been received, for evaluation of the underlying cause and confirmatory laboratory testing. More frequent monitoring of the liver tests should be initiated.

Discontinuation decisions will be made at each participating site by the Site Principal Investigator. If feasible, the process of discontinuation should be discussed with the Medical Monitor. The decisions regarding the discontinuation of the investigational therapy, whether the study medication should be stopped immediately or tapered should be discussed with the Medical Monitor, but final decisions about the process will remain at the discretion of the Site Principal Investigator.

Subjects who are discontinued from the clinical investigation for any reason will not be replaced.

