
Reason for Change: C-SSRS: More specific guidance how to utilize the C-SSRS instrument in assessing risk for suicide is provided. Specifically, patients with any suicidal behavior and/or suicidal ideation with intent or plan (ideation questions 4 and 5 in the C-SSRS) should be discontinued from the study and referred to psychiatric evaluation. Managing elevated LFTs: These stopping rules are intended to guide the investigator how to manage patients with elevated liver enzymes during the study. These stopping rules are in line with FDA’s recommendation on managing patients with elevated liver enzymes during clinical trials (Guidance for Industry: Drug-Induced Liver Injury: Premarketing Clinical Evaluation)
			
31	9.4.2 Identity of Investigational Products		
Added: All study medication will be labeled according to regional regulatory requirements. At minimum labels will contain the study number; a blinded bottle number; contents including quantity; dose and form; route of administration; storage conditions, instructions for study drug administration; caution that this compound is an investigative drug intended for clinical trial use only; warning to keep out of reach of children; and the identity of manufacturer and Sponsor. For those regions that require it, a blinded lot number and an expiry date will also be listed.

Reason for Change: Provided Investigational Product labeling content
			
33	9.4.5 Study Dosing and Dosage Adjustments, Open-Label Phase		
Subjects will start with 450 mg/d in divided doses BID for 3 days, 900 mg/d in divided doses BID for 3 days, 1350 mg/d in divided doses BID for 4 days, and 1800 mg/d in divided doses BID for 4 days until their Visit 6 (Table 2). At Visit 6, all subjects in both cohorts will be evaluated for tolerability and the investigator will make the determination to maintain the subject on 1800 mg/d or adjust their dose. Added: If the patient experiences any tolerability issues during the transition to OL, such as sedation or dizziness, changes to the titration schedule (e.g., conducting the titration over 3 weeks vs. 2 weeks) may be approved after discussion with the medical monitor.

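### Protocol 9.3.4.1 item 10d joins C-SSRS ideation questions 4 and 5 with 'and'; read literally, a subject positive on only one of them falls outside the mandatory withdrawal rule

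*Protocol*

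**What the plan says.** Section 9.3.4.1 of the protocol opens with a permissive lead-in: "The Investigator may discontinue subjects from the clinical study for any of the following reasons". Item 10 in that list has its own, mandatory lead-in: "Any subject who exhibits any of the following will be immediately withdrawn from the clinical investigation". Item 10d then names two triggers: any suicidal behavior on the C-SSRS, or a yes to "question 4 and 5 in the Suicidal Ideation section of the C-SSRS". A further sentence says that these patients should be sent for psychiatric evaluation immediately.

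Two other grounds in the protocol touch suicidality. Item 6 allows withdrawal of a subject who "no longer meets the inclusion criteria or develops any of the exclusion criteria". Exclusion criterion 15 in section 9.3.3 reads "Have active suicidal plan/intent, or have had active suicidal thoughts in the past 6 months".

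Appendix 8 gives the reason for the Amendment 4 change to this item. Besides patients with suicidal behavior, it says that those with "suicidal ideation with intent or plan (ideation questions 4 and 5 in the C-SSRS) should be discontinued from the study" and referred to psychiatric evaluation.

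On who applies the rule, section 9.3.4.1 says: "Discontinuation decisions will be made at each participating site by the Site Principal Investigator".

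**The concern.** The sentence uses 'or' to join behavior to ideation and then 'and' to join question 4 to question 5. A site can take that as a list of two qualifying answers or as one condition that needs both. The second reading leaves out a subject who reports some intention to act on suicidal thoughts but has not worked out a plan.

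For that subject, withdrawal would move from required to optional, and no sentence in the section would direct the site to refer. The rule is a patient-safety threshold applied locally at about 55 sites in six countries (protocol section 6), so the same answers could be handled differently from site to site.

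**Working it through.** There is no figure in the plan to reproduce. The check compares texts and works through the logic.

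**Inputs**
- Trigger wording and force: protocol 9.3.4.1, items 10 and 10d.
- The questions: Appendix 7, Since Last Visit form, which is used after randomization. A yes to question 2 leads to questions 3, 4 and 5, each with its own yes/no box. Question 4 is headed as intent without a specific plan, question 5 as a specific plan with intent.
- Fallback grounds: 9.3.4.1 items 6, 8 and 9, and 9.3.3 criterion 15.
- Stated purpose: Appendix 8, Amendment 4.

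**Step 1. The two readings, for a subject without suicidal behavior**

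| Q4 | Q5 | 'Either' reading | 'Both' reading |
|---|---|---|---|
| no | no | not triggered | not triggered |
| yes | no | triggered | not triggered |
| no | yes | triggered | not triggered |
| yes | yes | triggered | triggered |

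The readings differ in 2 of 4 patterns. Question 4 alone is the clearer case. Question 5 alone is possible because the two headings are nearly exclusive of each other. However, the spoken probe for question 4 asks only about intention, so a subject with plan and intent may well answer yes to both. The documents do not say how raters code this.

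**Step 2. What remains for a subject positive on one question only, under 'both'**
- Item 6 with criterion 15 applies, because the criterion covers intent as well as plan, and recent active suicidal thoughts too.
- Item 8 (an adverse event that warrants withdrawal) and item 9 (the subject's best interest, in the investigator's opinion) may apply.
- All three fall under the permissive lead-in, and none carries a psychiatric referral instruction.

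**Step 3. Which reading the documents favour**
- The Amendment 4 rationale glosses questions 4 and 5 as intent *or* plan: 'either'.
- Criterion 15 puts a slash between plan and intent: 'either'.
- The liver rule in the same section refers to "patients who must discontinue the study drug [a, b, c and d", where 'and' closes a list of alternatives: 'either' is natural usage here.
- Liver item 11c, however, uses 'and' to require a transaminase elevation together with a bilirubin elevation. Usage within the section is therefore mixed and does not settle item 10d.

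The balance is for 'either', but the text that settles it is in the amendment history, not in the rule.

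**Step 4. Who could be affected**
- Appendix 8 shows that the ideation trigger came in with Amendment 4, dated 8 April 2016. Amendment 3 is dated 23 September 2014.
- SAP 8.1 gives Cohort 1 a part-retrospective baseline, which protocol 9.5.1 ties to enrolment under or before Amendment 2.
- Cohort 1 participation is 4 + 9 + 52 + 2 = 67 weeks, or 67 × 7 = 469 days. From 23 September 2014 that runs to about 5 January 2016, roughly three months before Amendment 4.
- Unless Amendment 3 reached sites months late, Cohort 1 had finished. The wording therefore matters mainly for Cohort 2 assessments after April 2016.

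**The case against.** The best reply is that the protocol answers its own question. Appendix 8 is part of the document that sites hold, and it explains item 10d rather than contradicting it. The 'both' reading is also strained. The item speaks of a single yes answer, and with nearly exclusive headings a both-rule could miss even a subject with plan and intent, which no sponsor would want. Criterion 15 through item 6 reaches every subject with intent. The process of discontinuation is to be discussed with the Medical Monitor where feasible, the C-SSRS is meant for trained raters, and discontinued subjects return to their physician's care. Nothing shows that any site has read the rule as 'both'.

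Most of this stands, and it limits the point to wording. It does not remove it. Investigators act on section 9.3.4.1, and a suicide-risk rule should not have to be interpreted through an amendment log. The fallback grounds permit withdrawal but do not require it, and return to a physician's care is not a psychiatric referral.

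Stronger readings are tempting, but the documents do not support them:
- *The sponsor meant to keep intent-only subjects in the study.* The Amendment 4 rationale says the opposite.
- *Such subjects have no suicide-specific ground for withdrawal.* Item 6 with criterion 15 provides one.
- *Referral is mandatory under item 10d.* It is worded as 'should'; only the withdrawal is mandatory.
- *Each cohort has nine exposed assessments.* Appendix 1 does schedule nine C-SSRS assessments after randomization in each cohort, but Step 4 shows that Cohort 1 had probably finished before this wording existed. Cohort 2 subjects already on study by April 2016 had some of theirs behind them.

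**Conclusion.** The point holds as a drafting ambiguity in an operative safety rule. Taken literally, item 10d leaves a subject who is positive on only one of the two questions, and has shown no suicidal behavior, to the investigator's discretion and without the referral instruction. That is contrary to the sponsor's stated purpose.

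The size in subjects is unknown and is assumed to be small. SAP 9.8 plans to summarize and list C-SSRS answers by question and visit, so subjects positive on one question only could be counted. Different handling across sites is a possibility, not an observed fact. The point has no bearing on alpha, power, sample size or the efficacy analysis. The correction should be made because the rule protects patients and the change costs almost nothing.

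**What to change.** In item 10d, replace the ideation trigger with: *a yes answer to question 4 or question 5 (either or both)*, leaving the reference to the C-SSRS ideation section as it is. Keep the sentence on immediate psychiatric referral.

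This can go out in an amendment or a clarification letter to sites. It changes no visit, form, analysis or sample size. If 'either' was always the practice, nothing changes; if any site reads 'both', the gap is closed.
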